4.1 General Design

A mechanism oriented study, with within subjects design will be used. Healthy volunteer participants who are between 18 – 60 years old and meet basic eligibility criteria, will be offered participation in this study. Consenting participants will then undergo a baseline MRI scan in order to identify the exact location of the “Fitzgerald Target” in their DLPFC. Study staff will use FSL to analyze the images and communicate the coordinates via BrainSight to study coordinators. Participants will complete within subject comparisons and then will be randomized to a 3 arm study.

In the first phase participants will complete:

- 1) low-load condition vs high-load condition in the (cognitive) SST
- 2) low-load condition vs high-load condition in the (emotion) IAPS task

They will then complete again (in randomized order) with rTMS:

- 1) rTMS alone
- 2) rTMS + SST (cognitive)
- 3) rTMS + IAPS (emotion)

rTMS and the cognitive tasks will be conducted in the fMRI scanner where brain activation to a TMS probe and connectivity data will be obtained.

Finally they will be assigned to one of 3 groups to determine the effect of neuromodulation on DLPFC activation. Healthy participants will be randomized to one of 3 task conditions: high-load SST, high-load IAPS or low-load SST (sham task). Following a 4 session course of either active rTMS or sham rTMS neuromodulation (both active rTMS & Sham rTMS: at 120% RMT in triplet 50 Hz bursts, repeated at 5 Hz; 2 s on and 8 s off; 600 pulses per session; for a total duration of 3 min. and 9 s) in combination with one of

CONFIDENTIAL

the 3 task conditions participants will again have single pulse probes (120% RMT; 77 pulses/session) sessions in the scanner where DLPFC activation and connectivity will be determined. In this protocol we will use anatomically guided rTMS alone or in combination with tasks to test the hypothesis that cognitive paired associative stimulation results in augmented cortical response.

5 Study Population and Duration of Participation

25 healthy adults between the ages of 18 – 60 who meet inclusion/exclusion criteria will be asked to participate in approximately 7 study visits over the course of 3 – 4 weeks.

We estimate the following amount of time for each visit:

- Screening Visit: 2 hours
- Visit 1 - Baseline MRI Scan: 1 hour
- Visit 2 – Initial Task MRI Scan: 2 hours
- Study Visits 3 – 5: 2 hours each
 - Includes 1 hour MRI scan after Visit 4
- 7 – 14 day break pending participant availability
- Study Visits 6 – 8: 2 hours each
 - Includes 1 hour MRI scans before Visit 6 and after Visit 8

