Aim 3: to determine the effect of neuromodulation on DLPFC activation healthy participants will be randomized to one of the 3 task conditions: high-load cognitive SST, high-load IAPS task, or low-load SST (sham task condition). Following a 4 session course (2 session separated by at least 4 hours on one day, followed by 2 sessions separated by at least 4 hours on a second day) of either active rTMS or sham TMS neuromodulation in combination with the task condition participants will again have probe sessions in the scanner where DLPFC activation and connectivity will be determined. Following a 2-week interval, participants will receive the other stimulation condition (sham TMS if active first and active TMS if sham first).

[figure not shown]
Hypothesis 3a: Task (any of the 3) + active rTMS will result in greater DLPFC activation and greater dIPFC/sgACC anticorrelation than task plus sham rTMS

Hypothesis 3b: the IAPS task in combination with active rTMS will produce greater activation than the cognitive SST + active TMS or than control task + active TMS.

CONFIDENTIAL

4 Investigational Plan

Below is an example of the proposed study flow after screening visit. Please refer to attached task descriptions for further information:

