Does your study use MRI? (CAMRIS is the appropriate contact for all studies involving MRIs)

Yes No

Check of all that apply:

1.5T MRI
 3T MRI
 7T MRI

CONFIDENTIAL

Does the MRI use investigational sequences and/or coils?
(See Experimental Device Clause)

Yes No Unsure (if unsure you need to contact CAMRIS)

Does your study include pregnant women?
(See Pregnancy Clause and Justification)

Yes No

Does the MRI require the use of Contrast Agents?
(See Contrast Risks)

Yes No

Does your study involve the exposure to radiation, radiotracers and/or radiological imaging modalities?

Yes No (If No, no RRSC review is needed)

Ultrasound

Yes No

Will your study be using CT Scans? (CACTIS is the appropriate contact for studies involving CT scans)

Yes No

Below is a table that outlines what assessments and procedures will be completed at each visit:

Procedure	Screening Visit	Visit 1 Baseline MRI	Visit 2 Initial Task MRI	Visits 3 & 4	Visit 5	Visits 6 & 7	Visit 8
Clinical Assessments	X						
Self-Report Questionnaires	X			X		X	
MRI Scan		X	X		X		X
Behavioral Tasks		X	X	X	X	X	X
TMS (test pulse at Screening)	X		X	X	X	X	X

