6.2 Study Intervention Phase

6.2.1 MRI Visits

- Verify & sign MRI Safety Screening Form
- Undergo MRI with tasks
 - Baseline MRI – tasks in the scanner, no TMS probe
 - Visit 1 – tasks in the scanner with TMS

6.2.2 Prior to Baseline MRI – Randomized order of learning all 3 study tasks (SST, IAPS, and Sham) in the scanner without TMS.

6.2.3 Visit 1 – in the scanner participant completes all 3 tasks, in previously randomized order with TMS.

6.2.4 After Visit 1 – Randomized to SST task only, IAPS task only, or Sham task only & either Active rTMS + task or Sham rTMS + task

5.2.5 Neuromodulation & MRI Probe Visits:

- Visits 2 & 3: Complete randomized task alone & again with randomized rTMS group
 - Confidence rating
- Visits 4 & 5: Complete randomized task alone & again with opposite rTMS group
 - Confidence rating
- MRI probes: in the scanner, participant completes randomized task alone & then with TMS probe.

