7.7 Safety Evaluations

The primary investigator will routinely monitor and evaluate study procedures for potential increased risk.

8 Statistical Plan

Efficacy within subjects: Repeated measures ANOVA will be used to assess changes from baseline to post-stimulation for each task condition.

Efficacy between subjects: neuro-response rates and time to response will be compared with published rates within the literature to extrapolate the significance of this modality.

9 Safety and Adverse Events

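### Aim 3 (secondary), active/sham crossover: two washout rules, a pre-Visit 6 scan missing from the visit table, and an ANOVA with no period term or period-2 baseline

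*Combined protocol and SAP*

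**What the plan says.** **Washout.** The Study Summary and the Aim 3 text in Section 3.1 both say: "Following a 2-week interval, participants will receive the other stimulation condition". Section 5 instead lists a "7 – 14 day break pending participant availability".

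**Scans.** For Visits 6 to 8, Section 5 states: "Includes 1 hour MRI scans before Visit 6 and after Visit 8". The Section 6 table is introduced with "Below is a table that outlines what assessments and procedures will be completed at each visit". Its MRI row is marked at Visits 1, 2, 5 and 8, and the cell for Visits 6 and 7 is empty. Section 5 also puts the period-1 post-course scan after Visit 4, where the table has it at Visit 5.

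**Order.** Section 6.2.4 randomises participants to one task and to "either Active rTMS + task or Sham rTMS + task". The other condition follows: "Visits 4 & 5: Complete randomized task alone & again with opposite rTMS group". Those visit numbers are shifted from the table's.

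**Analysis.** The within-subject plan in Section 8, repeated in the Study Summary, is one sentence: "Repeated measures ANOVA will be used to assess changes from baseline to post-stimulation for each task condition".

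**The concern.** Hypothesis 3a (task plus active rTMS against task plus sham rTMS) is the trial's sham-controlled test of stimulation. Three features of a two-period crossover protect such a contrast: a washout long enough for the first course to fade, a defined baseline for each period, and an analysis that separates period from treatment. The plan contradicts itself on the first two and is silent on the third.

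The scan conflict matters most, because it decides what is estimated and a scan not taken cannot be recovered. With a pre-Visit 6 scan, each period can have its own baseline. Without it, the only pre-course scan with a TMS probe is Visit 2. Subtracting Visit 2 from both post-course scans removes it from the active-sham difference, so change from baseline becomes a plain contrast of post-course values. Which of the two is estimated would then depend on which section staff followed.

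Tasks and scans are repeated across periods, so a practice or habituation shift is plausible. An analysis without a period term puts that shift into the error and, if the sequences are unequal in size, into the estimate.

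**Working it through.** **1. Text check.** The two washout rules agree only at 14 days. The Section 5 minimum is 7/14 = half of the interval in Aim 3. Read against its header, the table's MRI row is: Screening blank, Visit 1 X, Visit 2 X, Visits 3 and 4 blank, Visit 5 X, Visits 6 and 7 blank, Visit 8 X. The pre-Visit 6 scan is absent. The table marks tasks but no TMS at Visit 1, and Section 6.2.1 says the baseline MRI has no probe. Visit 2 is therefore the only marked pre-course scan with a probe.

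**2. Inputs for size.** The documents give 25 participants but no alpha, power, effect size, SD, decay rate or period shift, so there is no figure to reproduce. Everything below is assumed: two-sided alpha 0.05, and an effect giving 80% power for a paired contrast at n = 25 (0.584 SD of the active-sham difference).

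**3. Washout.** Set the active effect to 1 and let it decay exponentially with half-life h. Visits 6 to 8 fall on consecutive days, so the period-2 post-course scan is 2 days after the break. The residue is g = 0.5^(break/h) at the pre-Visit 6 scan and f = 0.5^((break+2)/h) at the post-course scan. Only active-first participants carry it, and with equal sequences they are half the sample:
- post-course contrast = 1 - f/2
- own-baseline change contrast = 1 + (g - f)/2

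| h (days) | Post-course, 7 d | Post-course, 14 d | Change, 7 d | Change, 14 d |
|---|---|---|---|---|
| 1 | 0.999 | 1.000 | 1.003 | 1.000 |
| 2 | 0.978 | 0.998 | 1.022 | 1.002 |
| 3 | 0.938 | 0.988 | 1.037 | 1.007 |
| 7 | 0.795 | 0.897 | 1.045 | 1.022 |
| 14 | 0.680 | 0.774 | 1.033 | 1.024 |
| 30 | 0.594 | 0.655 | 1.019 | 1.016 |
| 60 | 0.549 | 0.584 | 1.011 | 1.010 |

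The largest gain from 14 rather than 7 days is 10.4 points for post-course values (h about 8 days). For change scores the difference is about 3 points at most.

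**4. Precision of the two baseline rules.** If pre- and post-course scan errors correlate rho, change scores have 2(1 - rho) times the variance of post-course values. For rho = 0, 0.25, 0.5 and 0.75 the ratio is 2.0, 1.5, 1.0 and 0.5, and 80% power becomes 51%, 63%, 80% and 98%.

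**5. Period term (simulated, 12/13 split).**

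| Shift (SD of difference) | Power without term | Power with term |
|---|---|---|
| 0.25 | 77% or 80% | 80% |
| 0.5 | 69% or 76% | 80% |
| 1.0 | 42% or 57% | 80% |

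The lower figure applies when the shift works against the larger sequence, the higher when it works in its favour.

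Without the term, the estimate moves by (n1 - n2)/(n1 + n2) of the shift: 1/25 = 4% at 13/12 and 7/25 = 28% at 16/9. At 16/9 with a 0.5 SD shift and no true effect, the bias is 0.28 × 0.5 = 0.14 SD. Type I error is then about 7% without the term and about 5% with it. If order were assigned by simple randomisation (no method is stated), a split of 16/9 or worse has probability 23%.

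**The case against.** - **The plan does not forbid a period factor.** This is true: a repeated measures ANOVA can include one, and a two-sentence plan names few terms of any kind. Because order is randomised, omitting period near balance costs precision rather than validity. This stands, and it limits the point to a correction.
- **Washout may hardly matter.** Under own-baseline change, the reading closest to Section 8, break length is almost immaterial in the table above. This also stands, but that analysis needs the pre-Visit 6 scan, which the table omits.
- **The missing flow figure may settle it.** It might show which scan precedes each course. But the text introduces it as an example ("Below is an example of the proposed study flow after screening visit"), and it would not remove the disagreement between the written rules.
- **The scan placements may be compatible.** A scan after Visit 4 may simply be the table's Visit 5. That is plausible but not stated, and this scan is the period-1 outcome.

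A reader might infer that the lower power figures are the expected loss. They are not: they hold in only one direction of the 12/13 split, and a 1.0 SD shift is about 1.7 times the assumed effect (1/0.584), with nothing in the documents to support it. A reader might also infer that no pre-course task data other than Visit 2 exist. Visit 1 has tasks in the scanner, but without a probe.

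**Conclusion.** The point holds for Aim 3 as a change that should be made. The two written conflicts (break length, pre-Visit 6 scan) and the two analytic gaps (period term, period-2 baseline) are plain from the text and rest on no assumption. The practical risk is a washout half as long as stated and a period-2 baseline that cannot be recovered.

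The sizes are only illustrative. They assume exponential decay, equal sequences for the washout figures, and the stated power set-up. On those terms, break length matters by up to about 10 points of the effect for post-course values and about 3 or less for change scores. The missing period term costs from almost nothing to 38 points of power (80% to 42%), depending on the shift and its direction.

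The documents do not support the stronger conclusion that the active-sham comparison is invalid or that carryover will bias it. They give no decay rate, order is randomised, and material type I inflation appears only with clearly unequal sequences. Nor would a period term repair carryover; only the washout and the baseline rule bear on that. The primary objective, which compares task loads without the crossover, is unaffected.

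**What to change.** 1. State one break with a 14-day minimum in the Study Summary, Aim 3 and Section 5, counted from the last session of course 1 to the first session of course 2.
2. Add the pre-Visit 6 scan to the Section 6 table, and give one position for the period-1 post-course scan.
3. Align the Section 6.2 visit numbers with the table, and reconcile 3–4 weeks (Section 5) with 5–7 weeks (Section 5.4).
4. Add a period term to the active-sham analysis pooled over the three tasks.
5. Name change from each period's own pre-course probe scan (Visit 2 and pre-Visit 6) as primary, with post-course values as a sensitivity analysis.

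**Cost.** Mostly wording; the scan is already in the Section 5 visit list. If there is no period shift, the term costs about 0.2 points of power in the pooled model. Within a task group of 8 it would take 80% to 78% at a 4/4 split and 66% at 2/6, so it belongs in the pooled model. Own-baseline change loses precision if pre/post correlation is below 0.5, which is why the post-course analysis is kept alongside it.

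The longer minimum reduces scheduling flexibility. With screening on day 1 and Visits 1 to 5 on days 2 to 6, Visit 8 falls on day 5 + 14 + 2 = 21 if the last course-1 session is Visit 4, or 6 + 14 + 2 = 22 if it is Visit 5. That fits 5–7 weeks (35–49 days) and is tight only at the 3-week end of 3–4 weeks.

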5.1 Inclusion Criteria

- Gender, inclusive
- 18 – 60 years of age
- Right-handed
- No history of meeting DSM criteria for any diagnosis
- Normal cognition
- Patients must be able to read and understand English
- Participants must be able to provide consent

5.2 Exclusion Criteria

- Pregnancy (Female participants)
- Outside age range
- Meets DSM criteria for any diagnosis
- Unable to have an MRI scan
- Medical condition that interferes with the collection or interpretation of MRI data
- Implanted devices such as: aneurysm clip or cardiac pacemaker
- History of stroke, epilepsy, or brain scarring
- Cognitive impairment
- Recent use of psychoactive medications, as determined by investigators
- Otherwise determined by investigator to be unfit for participation:
 - ex) Current alcohol or substance use disorder in last 3 months

5.3 Subject Recruitment

All participants will be recruited through the University of Pennsylvania and surrounding community. All subjects will express interest by initiating contact with the research staff for a center wide phone screening or self-screening procedure. All subjects fitting inclusion criteria will be approached by study staff to continue in the study. All subjects fitting inclusion criteria will be approached by study staff. This study will also be advertised on Facebook. These ads will be posted from the UPenn – Center for Neuromodulation in Depression and Stress Facebook page. They will be posted monthly and/or weekly. Study coordinators in the present study will use the results in REDCap as a source of recruitment, at which point those subjects will undergo the full phone-screen. This phone screen will also be collected and stored in REDCap. All recruitment materials, including but not limited to flyers, brochures, referral letters, online postings, and email templates will be IRB-approved before distribution of any of these material.

CONFIDENTIAL

5.4 Duration of Study Participation

We anticipate enrolling in the pilot for 6-months, but if the concept is proven after 6 months, for 2 years total. Each participant will be enrolled for 5 – 7 weeks, from the time of consent and screening to study completion. We anticipate this study will begin enrolling participants March 1, 2019.

5.5 Total Number of Subjects and Sites

We plan to initially enroll 25 healthy control patients at the University of Pennsylvania.

5.6 Vulnerable Populations: N/A

6 Study Procedures

A mechanism oriented study, with within subjects design will be used. Healthy volunteer participants who are between 18 – 60 years old and meet basic eligibility criteria, will be offered participation in this study. Consenting participants will then undergo a baseline MRI scan in order to identify the exact location of the “Fitzgerald Target” in their DLPFC. Study staff will use Brain Site to analyze the images and communicate the coordinates to study coordinators. Participants will complete within subject comparisons and then will be randomized to a 3 arm study.

In the first phase participants will receive:

- 1) a low load condition vs a high load condition in the SST
- 2) a low load condition vs a high load condition in the IAPS task

They will then receive in randomized order:

- 1) rTMS alone
- 2) rTMS + the SST or
- 3) rTMS + the IAPS task in randomized order.

rTMS and the cognitive tasks will be conducted in the fMRI scanner where brain activation to a TMS probe and connectivity data will be obtained.

Finally they will be assigned to one of 3 groups to determine the effect of neuromodulation on DLPFC activation. Healthy participants will be randomized to one of 3 task conditions: high-load SST, high-load IAPS or low-load SST (sham task). Following a 4 session course of either active iTBS or sham TMS neuromodulation (both iTBS & Sham: at 120% RMT in triplet 50 Hz bursts, repeated at 5 Hz; 2 s on and 8 s off; 600 pulses per session; for a total duration of 3 min. and 9 s) in combination with one of the 3 task conditions participants will again have single pulse probe (120% RMT; 77 pulses/session; 2.4 s each) sessions in the scanner where DLPFC activation and connectivity will be determined. In this protocol we will use anatomically guided TMS alone or in combination with tasks to test the hypothesis that cognitive paired associate stimulation results in augmented cortical response.

Although there are no known risks related to MRI on pregnant women or a fetus, there is a possibility of yet undiscovered pregnancy related risks. Since there is no possible benefit from participating in this protocol for a pregnant woman, we will exclude pregnant women. All women of child bearing potential are asked if they are using a reliable method of birth control and are required to attest that they are not pregnant before study visit and on the TMS safety screening form.

Does your study use MRI? (CAMRIS is the appropriate contact for all studies involving MRIs)

Yes No

Check of all that apply:

1.5T MRI
 3T MRI
 7T MRI

CONFIDENTIAL

Does the MRI use investigational sequences and/or coils?
(See Experimental Device Clause)

Yes No Unsure (if unsure you need to contact CAMRIS)

Does your study include pregnant women?
(See Pregnancy Clause and Justification)

Yes No

Does the MRI require the use of Contrast Agents?
(See Contrast Risks)

Yes No

Does your study involve the exposure to radiation, radiotracers and/or radiological imaging modalities?

Yes No (If No, no RRSC review is needed)

Ultrasound

Yes No

Will your study be using CT Scans? (CACTIS is the appropriate contact for studies involving CT scans)

Yes No

Below is a table that outlines what assessments and procedures will be completed at each visit:

Procedure	Screening Visit	Visit 1 Baseline MRI	Visit 2 Initial Task MRI	Visits 3 & 4	Visit 5	Visits 6 & 7	Visit 8
Clinical Assessments	X						
Self-Report Questionnaires	X			X		X	
MRI Scan		X	X		X		X
Behavioral Tasks		X	X	X	X	X	X
TMS (test pulse at Screening)	X		X	X	X	X	X

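### Within-session condition order is randomised with no stated balancing and run position is absent from the analysis, which costs precision in H2b and, depending on the run structure, in H2a and H1a

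*Combined protocol and SAP*

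**What the plan says.** Three places describe the order of the Aim 2 conditions. Section 6 introduces its list with "They will then receive in randomized order" and names rTMS alone, rTMS + SST and rTMS + IAPS. Section 4.1 gives the same three. Section 3.1 also randomises the order, but its list includes the task without TMS as well.

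Section 6.2 describes it differently. Section 6.2.2 has "Prior to Baseline MRI – Randomized order of learning all 3 study tasks (SST, IAPS, and Sham) in the scanner without TMS", and Section 6.2.3 says of the following visit: "in the scanner participant completes all 3 tasks, in previously randomized order with TMS". So Section 6.2 orders SST, IAPS and Sham, and carries one order per person from the no-TMS session into the TMS session. Aim 3 identifies the Sham task as low-load SST. Section 6.2.1 describes the first session as "Baseline MRI – tasks in the scanner, no TMS probe".

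Section 5.5 gives the sample size: "We plan to initially enroll 25 healthy control patients at the University of Pennsylvania". Section 8 gives the whole within-person analysis in one sentence: "Repeated measures ANOVA will be used to assess changes from baseline to post-stimulation for each task condition". It has no term for order, run position or period, and does not name the condition contrasts of Aims 1 and 2. The documents do not state how the orders are produced (simple, blocked or balanced).

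**The concern.** Practice, fatigue and scanner drift can change the response over the runs of a session. Randomising order guards against this, but with 25 people and six orders a simple draw can leave one condition earlier than another on average. If the analysis does not use run position, the drift also stays in the error of each within-person contrast. The contrasts at stake are:

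- **H2b** (rTMS + IAPS against rTMS + SST): exposed on any of the descriptions.
- **H2a** (rTMS with a task against rTMS alone): exposed if rTMS alone is one of the ordered conditions, as in Sections 4.1 and 6.
- **H1a** (high-load against low-load SST, a primary hypothesis): exposed if low-load SST is its own entry in the order, as Section 6.2.2 suggests.
- **H1b** (high-load against low-load IAPS): not exposed, because both loads lie inside the single IAPS entry.

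**Working it through.** The plan gives no alpha, power, effect size, SD or drift, so it has no figure to reproduce. From the documents: n = 25 and three ordered conditions, hence 3! = 6 orders. Assumed: simple randomisation, linear drift of d residual SDs from first to third run, and residual SD s = 1.

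**1. Position difference between two conditions.** Over the six orders it is −2, −1, −1, 1, 1, 2. The mean is 0, so there is no bias on average. The variance is (4+1+1+1+1+4)/6 = 2. With 25 people the mean position difference has SD √(2/25) = 0.283.

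**2. Loss of precision.** Drift per position is d/2, so it adds (d/2)² × 2 = d²/2 to a paired-difference variance of 2. The SE ratio is √(1 + d²/4).

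| d | SE ratio | Equivalent sample loss, 1 − 1/ratio² |
|---|---|---|
| 0.5 | √1.0625 = 1.03 | 6% |
| 1.0 | √1.25 = 1.12 | 20% |

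For H2a, taken as the mean of the two task conditions against rTMS alone, the position variance is 1.5 and the drift-free variance is 1.5. The ratio is again √(1 + d²/4).

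**3. Chance offset.** Its SD is √(d²/2/25), which is 0.07 or 0.14 residual SD. This is the same d²/2 as in step 2, seen in the estimate instead of the SE. It is not a second harm.

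**4. How uneven simple randomisation can be.** For a given pair, the chance of a split of 16:9 or worse in which condition came first is 2 × P(X ≥ 16) for X ~ Bin(25, ½), which is 0.23. In 200,000 simulated allocations, at least one pair was that uneven in 51%, some order was used at most once in 35%, and some order was never used in 6%.

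**5. Error rate and power.** The simulation used 40,000 runs per setting, an assumed two-sided alpha of 0.05 and an effect of 0.6 SD of the paired difference. Here g is drift per position in those SDs; since d/2 = g√2, d = 2.83g.

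| g | d | Type I error, simple order, no position term | Power, simple order, no position term | Power, near-balanced order, position term |
|---|---|---|---|---|
| 0 | 0 | 0.050 | 0.82 | 0.82 |
| 0.2 | 0.57 | 0.049 | 0.79 | 0.82 |
| 0.3 | 0.85 | 0.050 | 0.75 | 0.82 |
| 0.5 | 1.41 | 0.052 | 0.65 | 0.82 |

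Balancing without a position term makes the test conservative: type I error is 0.043 at g = 0.2 and 0.018 at g = 0.5, with power of 0.80 and 0.67. A position term on simple random orders gives power of 0.80 to 0.81 throughout. The simulated term was linear (one degree of freedom).

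**6. Near-balance at 25.** Four full blocks of six sum to zero, and the 25th person adds at most 2 positions, so the largest mean imbalance is 2/25 = 0.08.

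**7. Reusing the order.** For a between-task contrast averaged over both scans, the imbalance SD is 0.283 with reuse and √(1/25) = 0.200 with fresh orders. For the same task with and without TMS, it is 0 with reuse and √(2 × (2/3)/25) = 0.231 with fresh orders, provided drift is the same in both scans.

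**The case against.** The strongest reply is that randomised order already does its job: no expected bias and a valid test. The loss depends wholly on a drift that nobody has measured, and at 0.5 residual SD it is 3% of the SE. In addition, Section 8 does not name a model for the Aim 1 and Aim 2 contrasts, so a missing covariate is a detail of an analysis still to be written. All of this stands, and it limits the point to precision. It does not remove it, because the position term is nearly free and belongs in that model when it is written.

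A reader might infer more than the documents support:

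- **That the orders are unbalanced.** The documents are silent. The gap is that no method is specified, and the figures in step 4 assume simple randomisation.
- **That drift biases the contrasts.** It does not on average, and type I error stays at 0.049 to 0.052.
- **That reusing the order is a defect.** The plan does not propose to average the two scans, and reuse protects same-task comparisons with and without TMS.
- **That the whole primary aim is affected.** H1b is not, and H1c is a correlation with arousal ratings. Sections 3.1, 4.1 and 6 describe low against high load as a comparison within each task, and run detail is left to attached task descriptions that are not in the document. Section 6.2.2 also speaks of the order of learning the tasks. H1a is therefore exposed only conditionally.

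**Conclusion.** The point holds as one of precision. The plan randomises condition order over six possible sequences for 25 people, specifies no balancing, and does not use run position in the analysis. Under an assumed drift of 0.5 to 1.0 residual SD from first to third run, the exposed contrasts carry a standard error 3% to 12% larger than necessary. With little drift the loss is negligible. The power figures also rest on an assumed alpha and effect size and are illustrative.

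The conflict over which conditions are ordered has to be settled first. An order drawn for SST, IAPS and Sham has no place for rTMS alone, so Section 6.2 as written cannot supply the order for the conditions in Sections 4.1 and 6. If the fuller list in Section 3.1 applies, there are more than three conditions and the count of six orders changes.

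**What to change.** 1. Reconcile Section 6.2 with Sections 3.1, 4.1 and 6: which conditions are ordered in each scan, whether low-load SST is a separate run, where rTMS alone falls, and whether the TMS scan reuses the order. Align the visit labels too: Section 6.2 makes Visit 1 the TMS scan, while the procedures table makes it the baseline MRI without TMS. Reuse may be kept.
2. With three ordered conditions, draw orders from a list in blocks of six, each order once per block. This gives four people per order, plus one.
3. In Section 8, name the within-person model for the Aim 2 contrasts, and for H1a where the loads are separate runs, and include run position (1, 2, 3) as a fixed effect. Do steps 2 and 3 together, since balancing without the position term makes the test conservative.

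The cost is a different randomisation list and two degrees of freedom. With 25 × 3 = 75 observations, the residual falls from 75 − 25 − 2 = 48 to 46. No extra scans or participants are needed.
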